Investigational treatment	Drug whose properties are being tested in the study as well as their associated placebo and active treatment controls (when applicable). This also includes approved drugs used outside of their indication/approved dosage, or that are tested in a fixed combination. Investigational treatment generally does not include other study treatments administered as concomitant background therapy required or allowed by the protocol when used in within approved indication/dosage
Medication number	A unique identifier on the label of each study treatment package which is linked to one of the treatment groups of a study
Other study treatment	Any drug administered to the patient as part of the required study procedures that was not included in the investigational treatment
Subject Number (Subject No.)	A unique identifying number assigned to each patient/subject/healthy volunteer who enrolls in the study
Period	A subdivision of the study timeline; divides stages into smaller functional segments such as screening, baseline, titration, washout, etc.
Randomization number	A unique treatment identification code assigned to each randomized patient, corresponding to a specific treatment arm assignment
Stop study participation	Point/time at which the patient came in for a final evaluation visit or when study treatment was discontinued whichever is later
Study treatment	Includes any drug or combination of drugs in any study arm administered to the patient (subject) as part of the required study procedures, including placebo and active drug run-ins. In specific examples, it is important to judge investigational treatment component relationship relative to a study treatment combination; study treatment in this case refers to the investigational and non-investigational treatments in combination.
Study treatment discontinuation	Point/time when patient permanently stops taking study treatment for any reason
Treatment group	A treatment group defines the dose and regimen or the combination, and may consist of 1 or more cohorts. Cohorts are not expanded, new cohorts are enrolled.
Variable	Identifier used in the data analysis; derived directly or indirectly from data collected using specified assessments at specified time points
Withdrawal of consent	Withdrawal of consent occurs only when a patient does not want to participate in the study any longer, and does not want any further visits or assessments, and does not want any further study related contact

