	20 mL	Week 48	Pre-dose
	20 mL	Week 60	Pre-dose
	20 mL	Week 72	Pre-dose
	20 mL	Week 84	Pre-dose
	20 mL	Week 96	Pre-dose
	20 mL	Every 12 weeks thereafter (W108,W120,W132, W144,W156,W168)	Pre-dose
	20 mL	End of Treatment	Anytime
Blood for BCR-ABL Mutation analysis by Sanger Sequencing	2.5 ml	Week 1 Day 1	Pre-dose
	2.5 ml	End of Treatment	Anytime
Blood for BCR-ABL Mutation analysis only for patients with mutations at W1D1	2.5 ml	Week 12	Anytime
	2.5 ml	Week 24	Anytime
	2.5 ml	Week 36	Anytime
	2.5 ml	Week 48	Anytime
	2.5 ml	Week 60	Anytime
	2.5 ml	Week 72	Anytime
	2.5 ml	Week 84	Anytime
	2.5 ml	Week 96	Anytime
	2.5 ml	Every 12 weeks thereafter (W108,W120,W132, W144,W156,W168)	Anytime

During the study, peripheral blood samples will be collected into PAXgene™ Blood RNA tubes for all RQ-PCR assessments. Detailed instructions for the collection, handling, and shipment of RQ-PCR and mutation samples are outlined in the [\[CABL001A2301 Laboratory Manual\]](#).

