10.1 Analysis sets

10.1.1 Full Analysis Set

The **Full Analysis Set (FAS)** comprises all patients to whom study treatment has been assigned by randomization. According to the intent to treat principle, patients will be analyzed according to the treatment and stratum they have been assigned to during the randomization procedure.

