10.4.3 Handling of missing values/censoring/discontinuations

Only patients with MMR at 24 weeks are considered responders. In other words, any patient who achieves MMR before 24 weeks, but is no longer in MMR at 24 weeks, will be considered as a non-responder in this primary analysis. Patients discontinuing the randomized treatment prior to 24 weeks due to any reason will be considered as non-responders.

One exception to the rule above is if the 24-week PCR evaluation is missing, but both a PCR evaluation at 16 weeks and a PCR evaluation at 36 weeks indicate MMR, the 24-week assessment is imputed as a 'Response'.

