10.5.2 Other secondary efficacy objectives

Unless otherwise stated the FAS will be used for the analysis of all other secondary efficacy endpoints. The exceptions are using the Molecular Responder Set for duration of MMR and time to MMR, the CCyR Analysis Set for CCyR rates, and the Cytogenetic Responder Set for duration of CCyR and time to CCyR.

No statistical testing of non-key secondary efficacy endpoints will be performed, however a nominal p-value will be presented for exploratory purposes.

Molecular Response

MMR rates at scheduled time points (except 24 and 96 weeks which have been specified as primary and key secondary endpoints) will be evaluated in a similar fashion to the primary analysis of MMR rate at 24 weeks. Patients discontinuing the randomized treatment prior to a specific time point due to any reason will be considered as non-responders for that time point.

MMR rates by scheduled time points are defined as the proportion of patients who achieve MMR at or before the specified visit, i.e. if a patient achieves an MMR but then loses it before or at the visit, he/she will still be classed as achieving MMR by that time point.

For each endpoint the rate and the associated 95% confidence interval based on the Pearson-Clopper method will be presented by treatment group. Confidence intervals for the differences in any response rates between treatment groups will be provided using the Wald method.

Statistical testing will be performed via CMH chi-square tests stratified by the randomization strata. The Mantel-Haenszel estimate of the common risk difference and the corresponding 95% confidence interval will also be provided.

Duration of MMR is defined in [Section 7.2.1.1](#) as the time between the date of the first documented MMR and the earliest date of loss of MMR, progression to AP/BC, or CML-related death for patients in the Molecular Responder Set. The time will be censored at the last molecular assessment (PCR) date on treatment for patients who have not experienced any of the above events.

Duration of MMR will be analyzed by K-M method and presented by K-M plots. The estimated rates of patients who are still responding at various time points will also be provided using K-M method.

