To compare additional parameters of the efficacy of asciminib versus bosutinib	
 ● Cytogenetic response rate (Complete, Partial, Major, Minor, Minimal, no response) at and by all scheduled data collection time points including 24, 48 and 96 weeks ● MMR rate at all scheduled data collection time points (except 24 and 96 weeks which are already covered by primary and key secondary endpoints) ● MMR rate by all scheduled data collection time points including 24, 48 and 96 weeks ● Time to MMR ● Duration of MMR ● Time to CCyR ● Duration of CCyR ● Time to treatment failure ● Progression free survival ● Overall survival 	Refer to Section 10.5.2
To compare the safety and tolerability profile of asciminib versus bosutinib	Type, frequency and severity of adverse events, changes in laboratory values that fall outside the pre-determined ranges and clinically notable ECG and other safety data (vital signs, physical examination)	
To characterize the PK of asciminib in the CML-CP population	Trough plasma concentrations, PK parameters in full PK group: C _{max} , T _{max} , AUC _{0-12h} , CL/F	
To assess the safety of asciminib when administered as treatment after bosutinib failure according to the 2013 ELN Guidelines	Type, frequency and severity of adverse events, changes in laboratory values that fall outside the pre-determined ranges and clinically notable ECG and other safety data (vital signs, physical examination)	Refer to Section 10.6

Objective	Endpoint	Analysis

Exploratory
 
To evaluate the influence of factors such as cytogenetic response at baseline, failure/intolerance to prior TKIs, line of therapy, gender, race and age on the effect of asciminib with respect to the primary efficacy endpoint
 
To explore the exposure-response relationships of asciminib; evaluate the effect of population covariates
 
To characterize mutations in the BCR-ABL1 gene at Week 1 Day 1, upon confirmed loss of molecular response and/or at end of treatment and examine their association with molecular and cytogenetic response for asciminib vs. bosutinib
	
Major Molecular Response (MMR) rate at 24 weeks
 
Exposure-safety and exposure-PD analyses
 
BCR-ABL1 gene mutations at Week 1 Day 1, upon confirmed loss of molecular response and/or at end of treatment as determined by Sanger Sequencing
	
Refer to Section 10.6

[REDACTED]
	
[REDACTED]
	

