4.3 Definition of end of study

The patients are treated in the study up to end of study treatment period defined as up to 96 weeks after the last patient receives the first dose or up to 48 weeks after the last patient has switched to asciminib treatment whichever is longer unless patients have discontinued treatment earlier. The end of the study, concluding the survival follow-up, will occur 5 years from the date when the last patient enrolled into the study receives the first dose of the randomized treatment.

The primary analysis (cut-off date) is defined as the date when all randomized patients have been on study treatment for 24 weeks ([Section 10.4](#)) or discontinued earlier. Subsequent to this

analysis, the primary clinical study report (CSR) will be developed. Following the cut-off date for the primary CSR, the study will remain open. Patients who are ongoing at the time of the primary analysis will continue to receive the assigned study treatments (asciminib or bosutinib) during the study treatment period as defined above. The end of study treatment analysis will be conducted with a cut-off date 30 days after the end of study treatment period to ensure all available treatment data from all patients in the study is analyzed and summarized in a CSR.

After the end of the study treatment period the assigned study treatment will be made available to patients who in the opinion of the Investigators are still deriving clinical benefit. This may be outside of this study through alternative options including, but not limited to, an expanded access/compassionate use /managed access program or access to commercial supplies in applicable countries.

Patients will be followed for survival and progression for up to 5 years from the date the last randomized patient receives the first study dose (irrespective of treatment switch for patients failing bosutinib). Information on subsequent treatments will also be collected. An updated analysis of OS and PFS will be performed at the end of the follow-up period in the final study CSR.

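### MMR rates at visits beyond the follow-up shared by all patients count planned end of treatment as non-response, so the late rates and risk differences shrink with the accrual calendar

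*Combined protocol and SAP*

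**What the plan says.** **Endpoint.** Section 10.5 and Table 3-1 list as a secondary endpoint "MMR rate at all scheduled data collection time points (except 24 and 96 weeks which are already covered by primary and key secondary endpoints". No last visit is named, and the Amendment 3 Table 3-1 keeps the same endpoint.

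**Denominator.** Section 10.5.2: "Unless otherwise stated the FAS will be used for the analysis of all other secondary efficacy endpoints". Under Section 10.1.1 the FAS "comprises all patients to whom study treatment has been assigned by randomization".

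**Scoring.** Section 10.5.2: "Patients discontinuing the randomized treatment prior to a specific time point due to any reason will be considered as non-responders for that time point". The glossary defines study treatment discontinuation as "Point/time when patient permanently stops taking study treatment for any reason". These rates are otherwise to be handled like the primary endpoint, for which Section 10.4.3 says "Only patients with MMR at 24 weeks are considered responders". The one imputation exception there concerns a missing Week 24 sample.

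**Schedule.** In Amendment 1, Table 7-2 continues RQ-PCR sampling after Week 96: "Every 12 weeks thereafter (W108,W120,W132, W144,W156,W168". In Amendment 3, Table 7-1 replaces that list with 12-weekly visits to the end of study treatment.

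**End of treatment.** Section 6.1.5 fixes no duration per patient. Section 4.3 of Amendment 3 has an "end of study treatment period defined as up to 96 weeks after the last patient receives the first dose", or 48 weeks after the last switch to asciminib if that is longer. In both versions the survival follow-up column of Table 7-1 contains no PCR.

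**The concern.** Each rule is ordinary on its own. Together they put patients in the denominator of a late visit who could not have had a sample there. Such a patient may have been in MMR at the last on-treatment test and was stopped only because the treatment period closed, yet is scored as a failure.

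Section 10.5.2 treats the same patient differently for duration of MMR, where someone without an event is censored at the last on-treatment PCR. One report could therefore show sustained response by Kaplan-Meier beside a falling series of MMR rates and a narrowing difference between arms. That fall would come from entry dates, but a reader could take it for lost response.

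**Working it through.** **1. The plan's own figures.** Section 10.8 gives 222 patients (148 + 74) for 15% versus 35%, two-sided 5%, 90% power, 2:1. The pooled-variance formula without continuity correction returns 74 + 148 = 222. For Week 96, Table 10-2 gives 30% versus 53% at 90% power:

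- pooled rate = (74 × 0.30 + 148 × 0.53)/222 = 0.453
- SE under the null = √[0.453 × 0.547 × (1/74 + 1/148)] = 0.0709
- SE under the alternative = √[0.21/74 + 0.2491/148] = 0.0672
- z = (0.23 − 1.96 × 0.0709)/0.0672 = 1.35, power 91%, consistent with the stated 90%.

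I use 53% and 30% below only as a convenient starting pair. In the plan, 53% is a detectable rate, not a forecast.

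**2. Share of patients able to reach a visit.** Let treatment end E weeks after the last first dose and let accrual be uniform over A weeks. The share whose week-w visit falls on or before the end is q = 1 − (w − E)/A, kept between 0 and 1. Entry date does not depend on arm, so q is the same in both.

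**3. Rates under the written rule.** If no response is lost and nobody drops out for other reasons, the expected FAS rate is p × q, the difference is 23 × q points, and the ratio stays 0.53/0.30 = 1.77. With E = 96:

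| Visit | A = 52 weeks | A = 72 weeks | A = 96 weeks |
|---|---|---|---|
| W108: q | 77% | 83% | 88% |
| W108: rates | 40.8% v 23.1% | 44.2% v 25.0% | 46.4% v 26.3% |
| W108: difference | 17.7 | 19.2 | 20.1 |
| W132: q | 31% | 50% | 63% |
| W132: rates | 16.3% v 9.2% | 26.5% v 15.0% | 33.1% v 18.8% |
| W132: difference | 7.1 | 11.5 | 14.4 |

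**4. A rough check on accrual.** The documents give no accrual period. The amendment rationales report 38 patients randomised by 29 June 2018 and 86 by 21 November 2018: 48 patients in 145 days (20.7 weeks), or 2.3 per week. At that pace 222 patients take about 222/2.32 = 96 weeks, the upper end of the range. Whether the pace held is unknown.

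**5. A later end date.** Under Amendment 3 a patient may switch up to 96 weeks after the last randomisation, and treatment then runs 48 weeks after the last switch. At the extreme, E is about 96 + 48 = 144. Every patient can then reach W144, and the effect begins at W156, where q = 1 − 12/A is 77%, 83% or 88% for A = 52, 72 or 96.

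**6. With the denominator restricted.** Counting only patients able to reach the visit returns 53% versus 30% and 23 points throughout, under the same assumptions. With A = 72 and E = 96 the denominators are about 123 and 62 at W108, and 74 and 37 at W132.

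**The case against.** **The wording may be superseded.** The rule is read from the Amendment 1 protocol. The Amendment 3 text available here stops in Section 7.1.2, and the change logs show that Section 10.5.2 was edited in both later amendments. The Amendment 3 rationale also adds a rule that ELN treatment failure counts as non-response from then on. No log entry mentions planned end of treatment, but silence in a log is weak evidence. This stands and lowers confidence.

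**A planned end may not be a discontinuation.** Section 4.3 of Amendment 3 separates the end of the treatment period from earlier discontinuation, and it makes the assigned drug available afterwards to patients still benefiting. A visit after that date might also be called unscheduled for that patient. These readings are fair, but they do not settle the derivation. The set is still the FAS, the rates still follow the primary rule that only patients in MMR at the visit respond, and no study PCR is taken afterwards. The text gives no smaller denominator.

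**Little hangs on it.** Largely true. These are non-key secondary endpoints without formal testing. Section 10.7 names no MMR time point after Week 96, and durability has its own Kaplan-Meier endpoint.

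**Stronger readings that a reader might infer.** One is that MMR rates will fall to zero by Week 168. That needs 72 weeks of accrual, deduced from the last visit listed in Amendment 1 (168 − 96), so the zero is built in, and Amendment 3 dropped the list. Another is that the cumulative-incidence display and the 'by' rates share the fault. Neither can fall when treatment ends, because earlier responders stay counted. They can at most miss later responses, so no different estimator is required on this ground.

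**Conclusion.** The point holds for MMR rates 'at' visits beyond the follow-up common to all patients, on Section 10.5.2 as it reads in Amendment 1. Absolute rates and the Wald and Mantel-Haenszel risk differences are multiplied by the share of patients able to reach the visit. Under the illustrative assumptions (uniform accrual over 52 to 96 weeks, end 96 weeks after the last first dose, 53% versus 30% maintained, no other dropout), 23 points become about 18 to 20 at Week 108 and 7 to 14 at Week 132. With a treatment end 144 weeks after the last first dose, nothing happens until after Week 144. These figures are not a forecast.

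A reader might go further and doubt the primary or key secondary result, or suspect bias towards asciminib. The documents support neither. Every patient can reach Weeks 24, 48 and 96. The mechanism is the same in both arms, preserves the rate ratio, and shrinks the difference rather than creating one. Duration of MMR is also untouched. Confidence is moderate, because the current Section 10 needs to be checked.

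**What to change.** First check Section 10.5.2 of Amendment 3 and the SAP. If the rule is unchanged:

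- Limit FAS-based 'MMR rate at' visits to those that every randomised patient is scheduled to reach before the end of the study treatment period.
- For later visits, use as denominator the patients randomised early enough for the visit to fall on or before that date, and report n by arm. Patients in that denominator who stop early remain non-responders.
- State that reaching the planned end of study treatment is not a discontinuation under this rule.

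The cost is a few sentences of SAP text and one derived flag per patient and visit, with no new data. Late visits will have smaller denominators and wider intervals. With 53% versus 30%, the 95% half-width of the difference is about 1.96 × 0.0672 = 13 points on the full FAS. It grows as 1/√q, to about 17 points at Week 132 with 96 weeks' accrual (q = 0.625) and about 24 with 52 weeks' (q = 0.308). That width reflects the information actually available at those visits.

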- 10 out of 31 (32.3%) patients achieved MMR by 6 months
- 12 out of 31 (38.7%) patients achieved MMR by 9 months
- 13 out of 30 (43.3%) patients achieved MMR by 12 months
- At the dose of 40 mg BID, MMR was achieved in 1 out of 17 (5.9%) patients by 3 months, 4 out of 11 (36.4%) patients by 6 months, 5 out of 11 (45.5%) patients by 9 and 12 months

Cytogenetic response:

- 22 patients had $>35\%$ Ph+ metaphases at screening. Of these 22 patients, 5 patients were evaluable with 2 PCyR and 3 CCyR by 3 months. By 6, 9 and 12 months, 7 patients were evaluable with 1 minor cytogenetic response and 5 CCyR.
- 33 patients did not have CCyR at screening. Of these 33 patients, 7 patients were evaluable with 3 PCyR and 4 CCyR by 3 months. By 6, 9 and 12 months, 10 patients were evaluable with 1 minor cytogenetic response, 1 PCyR and 7 CCyR.
- 15 of the above 33 patients who did not have CCyR at screening were treated at the dose of 40mg BID. Of these 15 patients, 3 patients were evaluable and with PCyR by 3 months. By 6, 9 and 12 months 4 patients were evaluable with 1 PCyR and 2 CCyR.

Please refer to the latest [ABL001 Investigator's Brochure] for more details.

Safety:

ABL001 was generally well tolerated in heavily pre-treated CML patients resistant to or intolerant of prior TKIs. By data cutoff of 2 May 2016, 67 CML patients, including those with a T315I mutation (n=9), have been treated at any dose of the ABL001 BID regimen.

There were no study drug related deaths reported. One death was reported due to general physical health deterioration unrelated to the study drug. Overall, 43 SAEs were reported in 20 patients of the 67 patients. Six patients (9%) discontinued ABL001 due to adverse events. Dose limiting toxicities in the study included acute cardiac syndrome, lipase increase, arthralgia/myalgia, and bronchospasm in 1 patient each.

Overall of 67 CML patients, almost all (94%) patients reported at least one AE, including 45% reported grade 3/4 AEs. The most common AEs (>10%), regardless of study drug-relationship, were headache, increased lipase (23.9%), rash (20.9%), arthralgia, vomiting (both 19.4%), diarrhea, fatigue (both 17.9%), abdominal pain, pruritus (both 16.4%), constipation, myalgia, nausea, upper respiratory tract infection (all 14.9%), thrombocytopenia (13.4%), peripheral edema (11.9%), increased amylase, dizziness, musculoskeletal pain (all 10.4%).

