10.4.2 Statistical hypothesis, model, and method of analysis

The MMR rate at 24 weeks will be calculated based on the FAS and according to the Intent To Treat (ITT) principle. MMR rate and its 95% confidence interval based on the Pearson-Clopper method will be presented by treatment group. The confidence interval for the difference in MMR rate between treatment groups will be provided using the Wald method.

The null hypothesis is that there is no difference between the treatment groups with respect to MMR rate at 24 weeks. The Cochran-Mantel-Haenszel chi-square test, stratified by the randomization stratification factor, i.e. major cytogenetic response status (PCyR or CCyR vs others) at screening, will be used to compare MMR rate between the two treatment groups, at the two-sided 5% level of significance. The Mantel-Haenszel estimate of the common risk difference and the corresponding 95% confidence interval will also be provided.

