10.8 Sample size calculation

To test the null hypothesis that the response rate is equal in the two groups, based on two-sided 5% level of significance and with 90% power, 222 patients will be needed in total (i.e. 148 patients in the ABL001 arm and 74 patients in the bosutinib arm based on 2:1 randomization allocation). This assumes that ABL001 leads to a 20% improvement in the MMR rate at 24 weeks over bosutinib from 15% to 35% which corresponds to an odds ratio of 3.05.

The assumed bosutinib MMR rate of 15% at 24 weeks is based on previous trials evaluating bosutinib therapy ([Khoury 2012](#), [Gambacorti-Passerini 2014](#), [García-Gutiérrez 2015](#)).

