Efficacy assessments	Molecular response (RQ-PCR, mutational analysis) Cytogenetic response (Bone Marrow Aspirate)
Safety assessments	
 • Physical examination • Vital Sign • Height and weight • ECOG performance status • Laboratory chemistry and hematology • Serology • Electrocardiogram (ECG) • Echocardiogram • Pulmonary function tests with DLCO
Other assessments	
 • PK sampling (full/sparse) • Bone Marrow Biopsy • Patient Report Outcomes (MDASI-CML, PGIC, WPAI, EQ--5D-5L, resource utilization)
Data analysis	
The primary efficacy variable of the study is the Major Molecular Response (MMR) rate at 24 weeks. A patient will be counted as having achieved MMR at 24 weeks if he meets the MMR criteria (BCR-ABL1 ratio $\leq 0.1\%$) at 24 weeks.
 
The MMR rate at 24 weeks will be calculated based on the FAS and according to the Intention To Treat (ITT) principle. MMR rate and its 95% confidence interval based on the Pearson-Clopper method will be presented by treatment group. Confidence interval for the difference in MMR rate between treatment groups will be provided using the Wald method.
 
The Mantel-Haenszel estimate of the common risk difference and the corresponding 95% confidence interval will also be provided.
 
The key secondary endpoint is MMR rate at 96 weeks.
 
Formal statistical testing of the key secondary endpoint will be performed only if the primary endpoint is significant by means of a gatekeeping procedure to control the overall alpha level.

Key words	Phase III, open-label, randomized trial, asciminib, bosutinib, CML-CP, prior treatment with 2 or more TKIs

Amendment 3 (14-Dec-2018)

Amendment rationale

As of 21-Nov-2018, 137 patients were screened and 86 patients were randomized in the study, the study is currently ongoing.

The primary purpose of the amendment is:

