 - Section 10 Statistical methods and data analysis: precisions provided regarding the cut-off dates for the primary and end of study treatment phase analysis.
 - Section 10.1.5 Pharmacokinetic analysis set: precision provided on the post and pre-dose samples and vomiting.
 - Section 10.1.6 Other analysis sets: precision of MMR and CCyR responder sets.
 - Section 10.5.1.1 Analysis of key secondary objectives: adding an imputation rule for the secondary objective at 96 weeks and clarification concerning the analysis of the key secondary endpoint at week 96 if statistical significance is not reached for primary endpoint at week 24.
- [REDACTED]

[figure not shown]
- Section 10.5.2 Other secondary efficacy objectives: update of descriptive statistics definition and removal of presentation of p value as no formal statistical testing will be performed.
- Section 10.6.1 Exploratory efficacy objectives and Section 10.6.3 Exploratory biomarker objectives:
 - Correction of time points for BCR-ABL1 mutation characterization (baseline corrected to Week 1 Day 1, adding “upon confirmed loss of MMR, and changed “and” to “and/or” End of treatment).
 - [REDACTED]
- Section 10.6.4.1 Resource utilization: correction on duration of resource utilization reporting.
- Section 10.7 Interim analysis: clarification concerning the analysis of the key secondary endpoint at week 96 if statistical significance is not reached for primary endpoint at week 24.
- Section 14 Appendices: the lists of concomitant medications for patients on asciminib and bosutinib have been updated based on the internal Pharmacokinetic Sciences memorandum on Drug-Drug Interaction (release date: January 2018).
- Some minor inconsistencies (discrepancies between sections, typos) have been corrected.

IRBs/IECs

A copy of this amended protocol will be sent to the Institutional Review Board (IRBs)/Independent Ethics Committee (IECs) and Health Authorities.

The changes described in this amended protocol require IRB/IEC approval prior to implementation.

The changes herein affect the Informed Consent. Sites are required to update and submit for approval a revised Informed Consent that takes into account the changes described in this protocol amendment.

Amendment 1 (10-Apr-2017)

Amendment rationale

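### The Wald interval for between-arm response differences overstates certainty at sparse early MMR visits; a stratified score interval would repair this at almost no cost

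*Combined protocol and SAP*

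**What the plan says.** The full statistical section available is Section 10 of the Amendment 1 protocol. Section 10.4.2 states for the primary endpoint: "The confidence interval for the difference in MMR rate between treatment groups will be provided using the Wald method". Section 10.5.1.1 does the same for MMR at Week 96. Section 10.5.2 extends the method to the other molecular and the cytogenetic endpoints: "Confidence intervals for the differences in any response rates between treatment groups will be provided using the Wald method". None of these sections has a fallback for small counts.

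The same sections also plan:

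- exact Clopper-Pearson intervals for each arm's rate;
- a CMH test stratified by major cytogenetic response at screening;
- a Mantel-Haenszel common risk difference with its own 95% interval, whose variance formula is not named.

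The supplied Amendment 3 protocol stops before its Section 10. Its protocol summary keeps the method for Week 24: "Confidence interval for the difference in MMR rate between treatment groups will be provided using the Wald method". The Amendment 2 list of changes records, for Section 10.5.2, "removal of presentation of p value as no formal statistical testing will be performed". Neither the Amendment 2 nor the Amendment 3 list mentions a change of interval method.

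MMR is reported at and by all scheduled visits, and Table 7-2 of the Amendment 1 protocol schedules PCR at Weeks 4, 8, 12 and 16. On likely early rates, Section 1.2.1.2 of that protocol says that at 40 mg BID "MMR was achieved in 1 out of 17 (5.9%) patients by 3 months".

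**The concern.** The Wald interval estimates each arm's variance from its own observed rate. An arm with no responders contributes no variance at all, and with no responders in either arm the interval shrinks to a point. At 2:1 allocation the smaller bosutinib arm is the more likely to have none, so the error leans towards asciminib. The plan guards against small counts in the single-arm rates, where it uses exact intervals, but not in the comparison.

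At stake is how the early MMR comparisons read. These visits carry no formal test, and if the nominal p-values were dropped as the Amendment 2 list says, readers will judge the comparison from the intervals. An interval that only just excludes zero then looks like evidence of an early difference where a test would not find one.

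**Working it through.** **Inputs.** Section 10.8 gives the design: "based on two-sided 5% level of significance and with 90% power, 222 patients will be needed in total", with "148 patients in the ABL001 arm and 74 patients in the bosutinib arm based on 2:1 randomization allocation", for a "20% improvement in the MMR rate at 24 weeks over bosutinib from 15% to 35% which corresponds to an odds ratio of 3.05".

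**Reproducing the plan's figure.** With pooled variance, no continuity correction and 2:1 allocation, the pooled rate is (2 × 0.35 + 0.15)/3 = 0.2833. The bosutinib arm needs [1.96 × √(1.5 × 0.2833 × 0.7167) + 1.2816 × √(0.35 × 0.65/2 + 0.15 × 0.85)]² / 0.20² = (1.082 + 0.629)²/0.04 = 73.2, so 74. The total is 3 × 74 = 222, as stated; power is 90.3%.

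**Formulas.** Let x₁, x₂ be the responders, p₁ = x₁/148, p₂ = x₂/74 and d = p₁ − p₂.

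- Wald: d ± 1.96 × √[p₁(1 − p₁)/148 + p₂(1 − p₂)/74].
- Single-stratum CMH statistic on 1 df: (N − 1)(x₁ × non-responders₂ − x₂ × non-responders₁)² / (148 × 74 × responders × non-responders), with N = 222.

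**Example, 4 vs 0.** p₁ = 0.0270, and the bosutinib variance term is 0. The standard error is √(0.0270 × 0.9730/148) = 0.0133, so the interval is 0.0270 ± 0.0261, or +0.1 to +5.3 points. CMH is 221 × (4 × 74)²/(148 × 74 × 4 × 218) = 2.03, p = 0.15.

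**Other counts** (asciminib vs bosutinib; 95% intervals in points):

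| Responders | Wald | Miettinen-Nurminen | CMH p |
|---|---|---|---|
| 0 vs 0 | 0.0 to 0.0 | −5.0 to +2.5 | 1.0 |
| 4 vs 0 | +0.1 to +5.3 | −2.3 to +6.8 | 0.154 |
| 7 vs 0 | +1.3 to +8.2 | −0.3 to +9.5 | 0.058 |
| 8 vs 0 | +1.8 to +9.1 | +0.4 to +10.3 | 0.042 |
| 9 vs 1 | +0.1 to +9.4 | −1.6 to +10.1 | 0.110 |
| 39 vs 11 | +0.7 to +22.3 | −0.2 to +21.7 | 0.054 |
| 52 vs 11 | +9.1 to +31.4 | +8.2 to +30.8 | 0.0016 |

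With no bosutinib responders, Wald excludes zero from 4 asciminib responders; CMH needs 8. The 39 vs 11 row shows that disagreement can occur at larger counts too. The 52 vs 11 row is about the design rates.

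**Error when there is no true difference** (exact enumeration over all outcomes at 148:74; nominal 2.5% per side):

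| Common true rate | Wald excludes zero, favouring asciminib | Favouring bosutinib |
|---|---|---|
| 0.5% | 0.5% | 0.0% |
| 1% | 3.0% | 0.2% |
| 2% | 7.8% | 0.7% |
| 3% | 7.7% | 1.0% |
| 5% | 5.6% | 1.3% |
| 10% | 4.1% | 1.7% |

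The chance of 0 vs 0 is 33% at a common rate of 0.5%, 11% at 1% and 1% at 2%.

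**How often Wald and CMH would disagree.** The probability that Wald excludes zero while single-stratum CMH gives p ≥ 0.05 is 21% at 5.9% vs 2%, 12.5% at 14.3% vs 5%, and 2.2% at the design rates of 35% vs 15%. The 2% and 5% bosutinib rates are assumptions. The 5.9% and 14.3% are the phase 1 by-3-month rates in Section 1.2.1.2: 1 of 17 at 40 mg BID, and 6 of 42 across BID doses.

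**Does the Mantel-Haenszel interval help?** Not under the usual variances. With two strata and 20% to 40% of patients assumed in major cytogenetic response, both the Greenland-Robins and the Sato interval are 0 to 0 at 0 vs 0. At 4 vs 0 both exclude zero (lower limit 0.1 to 0.2 points), while the stratified CMH p is 0.14 to 0.16.

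**The case against.** Much of the case on the other side stands.

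- **Governing text.** The wording for early visits comes from Amendment 1. Amendment 3's Section 10 is not available, so it cannot be confirmed that Wald survives there for those visits. Only its Week 24 use is visible.
- **Benefit not inflated.** A reader might infer that the early intervals exaggerate asciminib's benefit. The documents do not support that. The point estimate is the same under either method, and at 4 vs 0 the Wald upper limit is lower than the score limit (5.3 against 6.8). At 5.9% vs an assumed 2%, Wald coverage is 94.9%. The 0 vs 0 collapse is false precision around no difference.
- **No conflict with a formal test.** A reader might also infer that the plan contradicts its own CMH test. At these visits that test is only nominal in Section 10.5.2, and the Amendment 2 list says its p-value was dropped. Formal inference at Weeks 24 and 96 rests on CMH.
- **Sparse counts not certain.** No Week 4 to 16 bosutinib rate is given, the pooled phase 1 rate was 14.3% by 3 months, and Amendment 3 admits up to 66 intolerant patients with BCR-ABL1 below 1%, who start nearer to MMR. At 8 vs 0 or 9 vs 0 the Wald, Miettinen-Nurminen and CMH results agree.
- **Cytogenetics.** Scheduled marrow assessments after screening start at Week 24, so the early-visit argument concerns MMR only.

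The objection that a Mantel-Haenszel interval is also reported does not stand: its variance is unspecified, and the usual choices fail at the same counts.

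**Conclusion.** The point holds as a minor reporting weakness. In the available text, the Wald interval is specified for every between-arm response difference with no small-count rule. If early MMR counts are sparse, it can collapse to zero width or exclude zero when CMH is not significant, and the error leans towards asciminib: about 4% to 8% of trials at common true rates of 2% to 10%, against 2.5%. At a 0.5% rate it falls to 0.5%.

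This rests on planned arm sizes of 148 and 74, on a single-stratum CMH for the tabulated p-values, on assumed early bosutinib rates, and on the Wald wording having survived into the later Section 10. At the design rates the effect is small: coverage is 94.6%, and Wald excludes zero against CMH in 2.2% of trials.

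**What to change.** In Sections 10.4.2, 10.5.1.1 and 10.5.2 and in the protocol summary, replace the Wald interval with a Miettinen-Nurminen score interval stratified by major cytogenetic response at screening. Report it as the single interval for the stratified difference, in place of both the Wald interval and the Mantel-Haenszel interval with unstated variance. Simply naming the Mantel-Haenszel difference as the main estimate would leave the sparse-count failure in place.

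Miettinen-Nurminen is preferable to Newcombe here because it agreed with the CMH result in every case tabulated. At 8 vs 0, Newcombe gives −0.2 to +10.3 points, which includes zero although CMH p = 0.042. In a single stratum the agreement is exact, because at zero difference the two statistics coincide; with two strata it should be close but depends on the weights, which the text should state.

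The cost is a wording change and a standard software option. Early-visit intervals become somewhat wider. The primary test, the sample size and data collection are unchanged.
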